6 EARLY DISCONTINUATION OF STUDY OR INDIVIDUAL SUBJECTS

6.1 Early Discontinuation of the Study and/or Site

The Sponsor has the right to terminate this study at any time. Reasons for terminating the study may include, but are not limited to:

- Incidence or severity of AEs in this or other studies indicating a potential health hazard to subjects.
- Unsatisfactory subject recruitment e.g., excessively slow
- Poor protocol adherence
- Incomplete or inaccurate data recording
- Poor compliance with the International Conference on Harmonization (ICH) guidelines for Good Clinical Practice (GCP)

In any instance of early discontinuation of the study, the Sponsor will notify, in writing, the Investigators, regulatory authorities and ethics committees, and will specify the reason(s) for termination.

6.2 Early Discontinuation of Individual subjects

Reasons for subject withdrawal from the study may include but are not limited to any of the following reasons:

- Subject withdrawal of consent
- Discretion of the Investigator, if it is deemed not safe, or in the subject's best interest, to continue
- Subject is lost to follow-up

The date and reason for discontinuation should be documented in the eCRF.

Subjects who discontinue the study should return to the site to complete the Early Termination visit assessments within 2 weeks (± 7 days) from the date of discontinuation.

6.3 Study Drug Discontinuation

Subjects should discontinue study drug for any of the following reasons:

- Malignancy: not including local and non-serious basal or squamous cell skin cancer
- Pregnancy
- Anaphylaxis, anaphylactoid or serious hypersensitivity reaction
- Grade 3 or higher rash
- Use of any medication to treat IPF, other than those documented at screening.
- AE, which in the opinion of the Investigator, precludes the subject from safely continuing in the study
- Pulmonary rehabilitation started at any time from screening until the end of the study
- Subject is noncompliant with study requirements

The date and reason for discontinuation should be documented in the eCRF.

Subjects who discontinue study drug *should continue in the study to complete all scheduled assessments.*

Those subjects who are unwilling or unable to complete all remaining scheduled assessments should return to the site to complete the Early Termination visit assessments within 2 weeks (± 7 days) from the date of discontinuation. In this way, all subjects will be assessed at least 5 half-lives after the last dose of study drug.

7 STUDY DRUG AND ACCOUNTABILITY

7.1 Study Drug

7.1.1 *Physical Description*

GBT440 is a synthetic small molecule bearing the chemical name 2-hydroxy-6-((2-(1-isopropyl-1H-pyrazol-5-yl) pyridin-3-yl) methoxy) benzaldehyde. The chemical formula is C₁₉H₁₉N₃O₃ and the molecular weight is 337.38.

7.1.2 Formulation

During this study GBT440 may be administered in the form of capsules or tablets as determined by the Sponsor

GBT440 Capsules: GBT440 will be provided as 300 mg capsules which contain GBT440 drug substance in Swedish orange, opaque, size 0, hypromellose capsules, along with several formulation excipients including hypromellose, microcrystalline cellulose, lactose monohydrate, croscarmellose sodium and magnesium stearate. All the excipients used for the formulation are also FDA IID (Inactive Ingredients Database) listed.

GBT440 Tablets: The GBT440 300 mg tablets contain GBT440 drug substance along with several formulation excipients. All the excipients used for the formulation are FDA IID listed.

7.1.3 Packaging and Labeling

GBT440 capsules will be supplied to the site in 100 mL bottles of 30 capsules. GBT440 tablets will be supplied to the site in 60 mL bottles of 30 tablets.

7.1.4 Supply

GBT or their representative will supply the packaged and labeled drug product to the investigational sites. Additional details are provided in the pharmacy manual.

7.1.5 Storage and Handling Procedure

All study medications will be stored at controlled room temperature between 15°C to 25°C protected from light in the storage area of the investigational site pharmacy, which is a secure, temperature-controlled, locked environment with restricted access.

No special procedures for the safe handling of GBT440 are required. The Sponsor will be permitted upon request to audit the supplies, storage, dispensing procedures and records.

7.2 Drug Accountability

In accordance with GCP, the Investigational Site will account for all supplies of GBT440. Details of receipt, storage, dispensing and return will be recorded. All drug received must be reconciled or explained.

All unused supplies of GBT440 will either be destroyed by the investigational site or returned to the study Sponsor's designee at the end of the study in accordance with instructions from the Sponsor.

Additional details are provided in the pharmacy manual.

8 DOSAGE AND TREATMENT ADMINISTRATION

8.1 Treatment Regimen

GBT440 will be administered orally each day for 90 days. GBT440 will be administered as 300 mg capsules or tablets.

Part A:

- GBT440 900 mg: three 300 mg capsules or tablets

Part B:

- GBT440 1500 mg: five 300 mg capsules or tablets

Instructions for administration of study drug:

- Self-administered by subject in the morning
- May be taken with or without food
- May be taken with water or another non-alcoholic beverage
- Swallow the capsules or tablets whole

Subjects must be instructed not to take study drug on the day of their scheduled visits (refer to the Schedules of Assessments provided in Appendix A [[Table 15-1](#) for Part A; [Table 15-2](#) for Part B]).

Study drug will be administered at the site on these days, after completion of all the assessments scheduled for that visit. The subject should be instructed to swallow the capsules or tablets whole.

If a subject misses a dose of the study drug, they should resume normal dosing the next day; i.e., on the next day, the dose of study drug should be unchanged — not increased or decreased.

8.2 Study Drug Dispensing

Study drug will be dispensed to subjects at each of the study visits (refer to the Schedules of Assessments provided in Appendix A [[Table 15-1](#) for Part A; [Table 15-2](#) for Part B]).

8.3 Dose Modification

Modification of study drug dosing may be considered if, in the opinion of the study Investigator, an AE may be possibly/probably related to study drug, and it would be unsafe for the subject to continue receiving their current dose of study drug.

The Investigator's assessment of AE relatedness should take into account the toxicity profile of all concomitant medications including pirfenidone and nintedanib.

Not all AEs require study drug modifications and may be managed as determined by the Investigator and based on the clinical nature of the AE.

The Sponsor's Medical Director should be contacted prior to any change in dosing.

8.3.1 Dose Adjustment

Dose adjustments may be initiated by the Investigator based on their assessment of the associated AE severity and overall subject safety.

The Investigator, in discussion with the Sponsor's Medical Director, may choose to reduce the total daily dose.

- The initial reduction in dose should be by one (300 mg) study drug capsule or tablet.
- A second dose reduction by another one (300 mg) capsule or tablet may be initiated, if deemed necessary by the Investigator and based on a safety assessment of the subject. The timing of the second dose reduction will be based on the Investigator's clinical assessment and in prior discussion with the Sponsor's Medical Director.
- Any further dose reduction deemed necessary by the Investigator should be by one (300 mg) capsule at a time and based on a safety assessment of the subject.

The Investigator must make every effort to return the subject to the dose level administered at the time of study enrollment.

Once, in the opinion of the study Investigator, it is safe to increase dosing, this may be performed by:

- Initiating the full dose, administered at study enrollment
- Increasing the dose in a step-wise fashion by single capsule or tablet increments. The timing of the increase in dosing should be at the discretion of the Investigator. Instructions for increasing study drug dosing are listed below.

Part A: If the subject is receiving a reduced dose of 300 mg (a total of 1 capsule or tablet) or 600 mg (a total of 2 capsules or tablets), the dose may be increased by 1 capsule or tablet (300 mg) at a time up to 900 mg (a total of 3 capsules or tablets) or a dose best tolerated by the subject.

Part B: If the subject is receiving a reduced dose of 300 mg, 600 mg, 900 mg or 1200 mg (a total of 1, 2, 3 or 4 capsules or tablets respectively), the dose may be increased by 1 capsule or tablet (300 mg) at a time up to 1500 mg (a total of 5 capsules or tablets) or a dose best tolerated by the subject.

Rash

In the case that a subject develops a rash, the Investigator must assess whether the rash might be due to study drug or concomitant medications, in particular pirfenidone or nintedanib which may both cause rash.

If, in the opinion of the Investigator, the rash may be possibly/probably related to study drug, the dose should be modified based on the instructions outlined in this section and in [Section 8.3.2](#).

An increase in dosing beyond the dose at the time of subject enrollment, is not allowed.

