8.3.2 Dose Interruption

Dose interruption may be initiated by the Investigator due to an AE, based on their assessment of the associated AE severity and overall subject safety and in discussion with the Sponsor's Medical Director.

Study drug should be restarted when, in the Investigator's opinion, it is safe to do so and in discussion with the Sponsor's Medical Director.

Part A

Study drug may be restarted at 900 mg (3 capsules or tablets) or at a lower dose (600 mg or 300 mg) as tolerated. If study drug is restarted at a lower dose the dose may be increased by 300 mg (1 capsule or tablet) at a time to a total of 900 mg (3 capsules or tablets) or a dose best tolerated by the subject. Refer to [Section 8.3.1](#) for instructions on dose escalation.

Part B

Study drug may be restarted at 1500 mg (5 capsules or tablets) or at a lower dose (900 mg, 600 mg or 300 mg) as tolerated. If study drug is restarted at a lower dose the dose may be increased by 300 mg (1 capsule or tablet) at a time to a total of 1500 mg (5 capsules or tablets) or a dose best tolerated by the subject.

For both Parts A and B, study drug may be discontinued due to an AE if, in the opinion of the Investigator, it is unsafe for the subject to continue receiving study drug. Subjects who discontinue study drug should remain in the study and complete all scheduled assessments (refer to [Section 6](#)).

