10.4 Discontinuation due to Adverse Events

Any subject who experiences an AE, serious or non-serious, may have study drug discontinued at any time at the discretion of the Investigator. The AE(s) should be noted on the appropriate eCRFs, and the subject's progress should be followed until the AE is resolved or stabilized as determined by the Investigator. The Sponsor's Medical Director and the CRO Medical Monitor must be notified. If the AE relates to overdose of study treatment, the IB should be consulted for details of any specific actions to be taken.

Subjects should return to the study to complete assessments as outlined in [Section 6](#).

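### For a drug-related rash of Grade 3 or higher, Protocol 6.3 says stop the drug, while the ungraded rash paragraph in 8.3.1 says modify the dose and leaves re-exposure open

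*Protocol*

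**What the plan says.** Protocol 6.3 opens its stopping list with "Subjects should discontinue study drug for any of the following reasons". One entry is "Grade 3 or higher rash", with no condition about cause. A separate entry covers adverse events that the Investigator thinks make it unsafe to go on, so the rash entry does not depend on that judgement.

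Protocol 8.3.1 has its own paragraph on rash. It applies to any rash, asks the Investigator to assess the cause, and says that if, in the Investigator's opinion, "the rash may be possibly/probably related to study drug, the dose should be modified based on the instructions outlined in this section" and in 8.3.2. It gives no grade and does not mention 6.3.

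The instructions it points to are these:

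- 8.3.1 provides reductions of 300 mg at a time. It adds: "The Investigator must make every effort to return the subject to the dose level administered at the time of study enrollment". The increase, stepwise or straight to the full dose, is to happen once the Investigator considers it safe.
- 8.3.2 provides interruption. "Study drug should be restarted when" the Investigator thinks it safe, in discussion with the Sponsor's Medical Director. For Part B, "Study drug may be restarted at 1500 mg (5 capsules or tablets) or at a lower dose"; Part A has the matching provision at 900 mg.
- 8.3.2 also says that "study drug may be discontinued due to an AE if, in the opinion of the Investigator, it is unsafe for the subject to continue receiving" drug. Section 10.4 is likewise permissive: a subject with an adverse event "may have study drug discontinued at any time at the discretion of the Investigator".

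**The concern.** A site managing a rash would naturally turn to the paragraph headed Rash in the dosing section. For a severe, drug-attributed rash that paragraph leads to dose modification, whereas 6.3 treats the same event as a reason to stop. A site could follow 8.3.1 faithfully and still breach 6.3, and two sites could handle the same event differently.

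What is at stake is re-exposure after a severe drug-related skin reaction. Rash is not a remote possibility for this drug. Protocol 1.5.1 names cough, diarrhea and rash as more frequent on GBT440 in sickle cell subjects dosed for 90 days, and says the Investigator considered diarrhea and rash treatment-related.

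**Working it through.** The question is one of text, so there is no figure to reproduce. Section 10.2.5 recognises two causality classes, not related and possibly/probably related. Crossing these with the grade cut-off in 6.3 gives four cases:

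| Rash | 6.3 rash entry | 8.3.1 rash paragraph | Conflict? |
|---|---|---|---|
| Grade 1-2, not related | silent | no modification called for | no |
| Grade 1-2, related | silent | modify dose | no |
| Grade 3+, not related | stop | no modification called for | no |
| Grade 3+, related | stop | modify dose | yes |

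The disagreement is confined to the last row.

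For that row, 8.3.1 and 8.3.2 between them offer three courses:

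1. **Reduce and continue.** One step down gives 900 − 300 = 600 mg in Part A or 1500 − 300 = 1200 mg in Part B. The subject stays on drug, contrary to 6.3.
2. **Interrupt, then restart** once judged safe, at a lower dose or the full dose. This is also contrary to 6.3.
3. **Discontinue**, if the Investigator thinks continuing is unsafe. This agrees with 6.3 but is worded as an option and is not tied to grade.

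Only the third course is consistent with 6.3, and the rash paragraph does not direct the reader to it.

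Next, does any text settle precedence?

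- 8.3, 8.3.1 and 8.3.2 neither limit the rash paragraph to lower grades nor cite the 6.3 rash criterion.
- 6.3 does not mention 8.3.
- The reference to Section 6 in 8.3.2 concerns staying in the study and completing assessments after stopping drug. The one in 10.4 likewise concerns completing assessments. Neither makes the 6.3 criteria override 8.3.
- The SAP (8.4.1) counts reductions, interruptions and permanent discontinuations but does not say which should follow a rash.

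No precedence statement was found in either document.

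**The case against.** The best case for the protocol is that the sections can be reconciled. Section 6.3 is a short stopping list with a graded trigger. Section 8.3 introduces dose modification as something that may be considered when the current dose is unsafe, so it can be read as covering subjects who may stay on drug. On that reading Grade 3 or higher rash stops under 6.3 and 8.3.1 handles the rest. Stopping the drug satisfies 6.3, and 8.3.2 allows it. This is the sensible reading and probably the intended one. It stands, but the reader has to infer it.

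Silence on precedence also proves little alone. Anaphylaxis is on the 6.3 list too, and nobody would read the general restart wording of 8.3.2 as overriding that stop. The stop is restated elsewhere for pregnancy (5.2, 10.5) and for escalation of IPF therapy (8.5.3), but no such restatement was found for malignancy or anaphylaxis, so restatement is not a convention of this protocol. Both points are fair. Rash differs because a paragraph names it and gives a different instruction.

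The safeguards are real. The 8.3.1 and 8.3.2 decisions start from the severity of the event and subject safety. The Medical Director should be contacted before any dose change (8.3) and takes part in the restart discussion (8.3.2). Rashes have a dedicated eCRF (Section 10), and allergic or hypersensitivity reactions of Grade 2 or higher are reported within 24 hours (10.2.3). These make an unconsidered restart unlikely, but none says which section governs.

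A reader might go further and infer that the protocol requires rechallenge after a severe rash, or that 8.3.1 was meant to override 6.3. The documents support neither. The effort to return to the enrollment dose is followed by a condition that increasing the dose is judged safe, restart carries the same condition, and a lower dose is allowed.

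**Conclusion.** The inconsistency is real but minor. For a rash that is both Grade 3 or higher and possibly/probably related to study drug, 6.3 says stop, while the rash paragraph in 8.3.1 says modify, under provisions that permit re-exposure up to the full dose once judged safe and make stopping optional. Reading 6.3 as controlling resolves it, but the rash-specific text does not say so.

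Its size cannot be put in numbers. The documents give no rate of Grade 3 or higher rash, and 1.5.1 describes the rashes seen so far as mildly itchy, resolving in 2 to 5 days and without systemic features. With up to about 32 subjects the case may never arise, so a prediction that subjects will be wrongly rechallenged would go beyond the evidence. No sample size, endpoint or error rate is affected.

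The conclusion rests on the protocol and SAP text alone. A site manual or training slide that settles the point would reduce its practical importance, though the protocol wording would still need correcting.

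**What to change.** Limit the 8.3.1 rash paragraph to Grade 1-2 rash and add a sentence such as: *Grade 3 or higher rash: discontinue study drug per Section 6.3; the restart and re-escalation provisions of 8.3.1 and 8.3.2 do not apply.*

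The cost is one or two sentences in a protocol amendment and a memo to sites, with no added procedures or subjects. The downside is slightly less Investigator discretion after a severe related rash, which 6.3 already withholds.

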8.3.2 Dose Interruption

Dose interruption may be initiated by the Investigator due to an AE, based on their assessment of the associated AE severity and overall subject safety and in discussion with the Sponsor's Medical Director.

Study drug should be restarted when, in the Investigator's opinion, it is safe to do so and in discussion with the Sponsor's Medical Director.

Part A

Study drug may be restarted at 900 mg (3 capsules or tablets) or at a lower dose (600 mg or 300 mg) as tolerated. If study drug is restarted at a lower dose the dose may be increased by 300 mg (1 capsule or tablet) at a time to a total of 900 mg (3 capsules or tablets) or a dose best tolerated by the subject. Refer to [Section 8.3.1](#) for instructions on dose escalation.

Part B

Study drug may be restarted at 1500 mg (5 capsules or tablets) or at a lower dose (900 mg, 600 mg or 300 mg) as tolerated. If study drug is restarted at a lower dose the dose may be increased by 300 mg (1 capsule or tablet) at a time to a total of 1500 mg (5 capsules or tablets) or a dose best tolerated by the subject.

For both Parts A and B, study drug may be discontinued due to an AE if, in the opinion of the Investigator, it is unsafe for the subject to continue receiving study drug. Subjects who discontinue study drug should remain in the study and complete all scheduled assessments (refer to [Section 6](#)).

8.3.3 Pirfenidone or Nintedanib Background Therapy

If, in the opinion of the Investigator, the subject experiences significant side effects, judged to be related to pirfenidone or nintedanib therapy, treatment of symptoms and/or dose modifications of these medications are allowed.

The decision to modify pirfenidone or nintedanib dosing is ultimately the responsibility of the Investigator. Any modifications to dosing will be managed by the Investigator throughout the study, taking in to account the United States Prescriber Information (USPI) of the drugs

and past history of care from the subject's IPF health care provider and must be entered into the eCRF.

8.4 Study Drug Overdose

To date, no events of overdose have been reported. Based on the mechanism of action of GBT440, the result of an overdose might include, but is not limited to, increased severity of previously reported associated AEs or decreased oxygen delivery to tissues (refer to [Section 1](#)). In the event of a medical emergency due to suspected GBT440 overdose, the Medical Monitor should be contacted as soon as possible.

8.5 Concomitant Medications

A concomitant medication is defined as any prescription or over-the-counter preparation, including vitamins and supplements.

In the interests of subject safety and acceptable standards of medical care the Investigator will be permitted to prescribe treatment(s) at his/her discretion. For all subjects, concomitant medications taken from signing of the informed consent until the last study visit must be recorded in the subjects' eCRFs.

All reported prior and concomitant medications will be coded using the WHO Drug Dictionary.

8.5.1 Permitted Therapy

Use of the following therapies is allowed during the study:

- Pirfenidone, nintedanib or N-acetylcysteine (NAC) for the treatment of IPF
 - Only if at the time of screening, the dose has been stable for at least 1 month prior to screening and with no anticipated need for dose adjustments during the study
- Corticosteroids for the treatment of IPF
 - Only if the dose at screening is ≤ 10 mg per day of prednisone (or an equivalent) and has been stable for at least 14 days prior to screening and with no anticipated need for dose adjustments, including reductions in dose, during the study
- Corticosteroids for the treatment of non-IPF conditions
 - Only if the dose of prednisone (or an equivalent) has been stable for at least 14 days prior to screening, and in the opinion of the Investigator not anticipated to require dose adjustments during the study
- Maintenance therapy for other medical conditions listed in the subject's medical history at the time of screening

Medications such as acetaminophen, non-steroidal anti-inflammatories and routinely-taken dietary supplements, including vitamins are allowed at the discretion of the Investigator and provided that the medications have no discernable impact on the study.

8.5.2 *Restricted Therapies*

Subjects should not take the following medications within 14 days prior to screening and during the entire study:

- Strong inducers of CYP3A4/CYP3A5, CYP2B6, CYP2C9 and CYP2C19 (refer to Appendix B; these medications may decrease the blood concentration of GBT440)
- Herbal medications (e.g., St. John's Wort)

The following medications should be used with caution:

- CYP3A4 substrates with a narrow therapeutic index (refer to [Table 8-1](#); GBT440 may increase the plasma concentration of these medications)

Table 8-1 CYP Substrates with Narrow Therapeutic Range

CYP Enzymes	Substrates with Narrow Therapeutic Range
CYP3A4	Alfentanil, astemizole, cisapride, cyclosporine, dihydroergotamine, ergotamine, fentanyl, pimozide, quindine, sirolimus, tacrolimus, terfenadine
Note that this is not an exhaustive list. For an updated listed, refer to the following link: http://www.fda.gov/Drugs/DevelopmentApprovalProcess/DevelopmentResources/DrugInteractionsLabeling/ucm093664.htm#4 Substrates with a 'narrow therapeutic range' refers to drugs whose exposure-response relationship indicates that small increases in their exposure levels by the concomitant use of CYP inhibitors may lead to serious safety concerns. Adapted from: FDA DRAFT Guidance for Industry: Drug Interactions Studies-Study Design, Data Analysis, Implications for Dosing, and Labeling Recommendations. February 2012.	

8.5.3 *Therapies for treatment of IPF*

Therapies, other than those used at the time of screening, for the treatment of IPF are not allowed.

If in the opinion of the Investigator an escalation in therapy for IPF is required, then study drug should be discontinued and the subject should complete all remaining scheduled assessments (refer to [Section 6.3](#)).

8.6 *Fertility/Contraceptive Requirements*

Highly effective birth control should be used from the screening period until 30 days following the last study drug administration.

8.6.1 *Acceptable Forms of Contraception*

Highly effective methods of birth control are considered acceptable in this study. Highly effective is defined as those methods of birth control which result in a low failure rate (i.e., less than 1% per year) when used consistently and correctly.

For female subjects:

- Combined (estrogen and progestogen containing) hormonal contraception associated with inhibition of ovulation:
 - Oral
 - Intravaginal
 - Transdermal
- Progestogen-only hormonal contraception associated with inhibition of ovulation:
 - Oral
 - Injectable
 - Implantable
 - **Note:** Hormonal contraception must be supplemented with a barrier method (preferably male condom).
- Intrauterine device (IUD)
- Intrauterine hormone-releasing system (IUS)
- Bilateral tubal occlusion
- Vasectomized partner. Note that vasectomized partner is a highly effective birth control method provided that partner is the sole sexual partner of the woman of child-bearing potential trial participant and that the vasectomized partner has received medical assessment of the surgical success.

For male subjects:

- Vasectomy
- Two acceptable methods of contraception: Must agree to use, at least one of which must be a barrier method (e.g., spermicidal gel plus condom) for the entire duration of the study, and for 30 days following last study drug administration.
- Sexual abstinence:

This method of contraception is considered highly effective only if the subject is refraining from heterosexual intercourse during the entire period of risk associated with the study drug. The reliability of sexual abstinence needs to be evaluated in relation to the duration of the clinical trial and the preferred and usual lifestyle of the subject.

